3.5 Participant timeline

Data for this study will be collected by the RA and entered into an electronic data platform supported by REDCap™ (Research Electronic Data Capture Vanderbilt University, Nashville, TN, USA) at three time points: (T1) at baseline (prior to procedures); (T2) during the procedure; and (T3) on hospital discharge.

After receiving participant consent, demographic information and eligibility to participate will be confirmed at T1. Transcutaneous carbon dioxide (TcCO₂) monitoring and pulse oximetry will be measured continuously at T2. Adverse sedation events, patient comfort with sedation, difficulty maintaining oxygen saturation and using the device, and cost associated with the oxygen delivery device will be assessed at T3. Patient satisfaction with sedation will also be assessed at this time using the Iowa Satisfaction with Anesthesia Scale (ISAS) through REDCap™.

	During Pre-procedure procedure	Post- procedure
--	---	----------------------------

TIMEPOINT	T1	T2	T3
ENROLLMENT:	X		
Eligibility screen	X		
Informed consent	X		
Allocation	X		
INTERVENTIONS:			
Facemask oxygen supplementation		X	
High flow nasal oxygen		X	
ASSESSMENTS:			
Demographic information and medical history	X		
Peak TcCO ₂ concentration		X	
Mean TcCO ₂		X	
Area under the curve of oxygen desaturation		X	
Adverse sedation events			X
Patient satisfaction with sedation			X
Costs associated with oxygen delivery			X
Anesthesia Assistant rating of difficulty maintaining the patient's oxygenation			X

status

Anesthesia Assistant rating of difficulty using oxygen delivery device	X
Patient comfort of oxygen delivery	X

3.6 Sample size

We estimate based on data from our preliminary study that the peak TcCO₂ level in the control group will be 47 mmHg and standard deviation in both groups will be 7 mmHg. Assuming a type I error rate of 5%, a sample of 130 participants would achieve 90% power to detect a reduction in mean TcCO₂ levels of 4 mmHg in the intervention period. A difference in TcCO₂ levels of 4 mmHg was selected for this sample size calculation because it was used to power previous randomized controlled trials of the effect of oxygen supplementation on ventilation status in other populations, with the authors noting that an effect of this magnitude was of physiological significance.^{16,17} Also, differences in CO₂ levels of a similar magnitude have been detected in previous trials evaluating the efficacy of interventions to improve sedation safety.¹⁸⁻²² To account for any missing primary outcome data (in the event that the TcCO₂ monitor malfunctions) and dropouts (in the event that a randomized patient's procedure is cancelled or anesthetic management plan is changed prior to procedure commencement), we plan to recruit a sample of 150 participants.

3.7 Recruitment

A Research Assistant (RA) will be engaged in this work performing the roles of eligibility screening/participant recruitment and data collection.

3.7.1 Pre-admission clinic recruitment process

Potential participants scheduled for a procedure in advance will be initially approached during their attendance at the pre-admission clinic. The RA will receive the pre-admission clinic and cardiac catheterization

laboratory schedules from the electrophysiology Nurse Practitioners to identify potential participants. Any potential participants that meet exclusion criteria will be flagged by the Nurse Practitioner at this time. The RA will inform the pre-admissions clinic nurse or administration assistant (i.e. someone within the patient's circle of care) about which patients are eligible for the study. The pre-admission clinic nurse or administration assistant will ask the potential participant for permission for the RA to provide additional information and invite them to participate in the study. If the potential participant agrees, the RA will explain the study and provide a Participant Information and Consent Form.

3.7.2 In-patient recruitment process

The RA will review the cardiac catheterization laboratory schedules to identify potential participants who have been admitted as in-patients. The RA will inform either the electrophysiology Nurse Practitioner (i.e. a healthcare professional within the patient's circle of care) or the patient's allocated Registered Nurse for the shift about which patients are potentially eligible for the study and ask them to check if they meet any of the exclusion criteria. If the patient is eligible, the Nurse Practitioner or Registered Nurse will ask the potential participant for permission for the RA to provide additional information and invite them to participate in the study. If the potential participant agrees, the RA will explain the study and provide a Participant Information and Consent Form the day prior to their scheduled procedure so that they can consider their participation overnight.

3.7.3 Same-day admission recruitment process (no attendance to pre-admission clinic)

A small proportion of the total number of eligible participants will be scheduled for a procedure but will not be attending the pre-admission clinic. An example would be a stable out-patient without major comorbidities attending for a permanent pacemaker generator change as a day procedure. If potential participants who are to be admitted on the day of their procedure without attending the pre-admission clinic are identified, the electrophysiology administration assistant or Nurse Practitioner who will be making contact with the participant to organise their admission, will ask the participant if they are willing to be contacted by a RA to provide further information about the study. If the

potential participant agrees to be contacted, The RA will use the standardised telephone script to explain the study to the participant and will ask if the participant would like a Participant Information and Consent form sent to them by mail or email. On the day of admission, the RA will confirm with the potential participant if they agree to participate and complete the consenting process.

3.7.4 Alternative process for recruitment on day of procedure (only if potential participants could not be contacted using the above processes)

All efforts will be made to make initial contact and explain the study to potential participants prior to the day of their procedure using the processes outline above. If this is not possible, in some circumstances there may be enough time for a potential participant to consider participating in the study on the same day as their procedure. For example, same-day admission patients who are scheduled to have their procedure in the afternoon still typically arrive to the hospital at 7am. In such circumstances, if an eligible participant has not been able to be contacted, the RA will inform the same-day admission unit's administration assistant, the electrophysiology Nurse Practitioner or the patient's allocated Registered Nurse for the shift about which patients are potentially eligible for the study and ask them if they meet any of the exclusion criteria. If the patient is eligible, the Nurse Practitioner or Registered Nurse will ask the potential participant for permission for the RA to provide additional information and invite them to participate in the study. If the potential participant agrees, the RA will explain the study and provide a Participant Information and Consent Form.

3.8 Allocation

Consented eligible patients will be allocated randomly to intervention and control groups. A stratified (by diagnosis of obstructive sleep apnea and type of procedure – cardiac resynchronization therapy device implant), block randomized sequence will be generated using the redcapAPI package in R and uploaded to REDCap™. The RA will retrieve the allocation for each consecutive participant in REDCap™ prior to the procedure.

3.9 Blinding (masking)

3.9.1 Blinding mechanism

Due to the nature of the intervention, participants or personnel involved in the trial cannot be blinded to the treatment conditions. Data will be collected in a fashion such that the primary outcome assessment for comparisons between groups will be made without knowledge of the assigned treatment allocation.

3.9.2 Emergency unblinding

Due to the nature of the intervention, participants or personnel involved in the trial cannot be blinded to the treatment conditions.

3.10 Data collection

3.10.1 Trial procedures and evaluations

Instruments used to measure outcomes

Transcutaneous carbon dioxide concentrations: PI [name] will provide training to the RA in use of the transcutaneous carbon dioxide monitoring device and other data collection procedures. The RA will attach the Sentec VSign 2 sensor to the participant's forehead using a multi-site attachment ring. Once the Sentec Digital Monitoring System displays a stabilized TcCO₂ level, the monitor will be covered with a drape so that it is not visible to research staff or clinicians during the procedure. The monitor will not be used by the clinicians to guide treatment. Data will be downloaded to a computer using the USB port on the monitor. TcCO₂ monitoring provides continuous, accurate (mean bias within 2 mmHg) and precise (95% limits of agreement within 6 mmHg) estimates of arterial CO₂ (PaCO₂) in sedated patients.¹⁴

Pulse oximetry: Percentage of hemoglobin saturated with oxygen (SpO₂) will be measured continuously throughout procedures as part of routine clinical practice through the anaesthetic machine. We will access the DREAM (Drug Reconciliation and Electronic Anesthesia Monitoring) system to download this data. Unreliable SpO₂ measurements will be filtered out if a pulse rate is not detectable.

Tracking and reporting outcomes of procedural sedation tool.²³ This tool was developed, using a consensus process, by members of a multidisciplinary society who had demonstrated capacity, dedication and competence in research and/or clinical experience in procedural sedation. Completion of the tool requires identification and description

of the adverse event, the intervention, the outcome and the overall severity of the adverse event. The Anaesthesia Assistant will be asked to complete this tool at the end of procedures. It takes approximately 2 minutes to complete.

Iowa Satisfaction with Anesthesia Scale (ISAS): The ISAS is a questionnaire that can be used to measure patient satisfaction with the anesthetic used during a procedure performed with sedation.^{24,25} Completion of the 11 items takes 4-5 minutes. This scale reliably measures the construct of satisfaction with the anesthetic, with a Cronbach alpha of .84 found in a 24-center, 315 patient placebo-controlled trial of dexmedetomidine.²⁵ In this study, the utility of the ISAS as an outcome measure for sedation trials was demonstrated, as it was able to differentiate patient satisfaction among patients. There were 47 different scores among the 315 participants. In addition, whereas 73% of patients responded with the minimum or maximum score for the single question “I was satisfied with my anesthetic”, only 14% of the sample scored the minimum or maximum for the ISAS.²⁵

Adverse effects: Adverse effects of delivering gas at a high flow rate through the nasal passages will be assessed. These include nose bleeding arising from damage to the mucosal surface and pressure injury to skin from the device. The RA will inspect intervention group participants' skin integrity around the nasal region at the end of procedures to assess for these potentially anticipated as well as unanticipated adverse effects.

Costs: Anesthesia Assistants will document devices used for supplemental oxygen delivery and airway management in both groups as per their usual practice in the DREAM anesthesia monitoring system. This data will be accessed for the study by downloading the report from the DREAM anaesthesia monitoring system, permitting the per-patient costs for oxygen delivery and airway management to be calculated and compared between groups.

Anesthesia Assistant rating of perceived level of difficulty in maintaining oxygenation: The Anaesthesia Assistant will be asked to rate their perceived level of difficulty in maintaining oxygenation using a 6-level rating scale with ratings of “extremely difficult”, “very difficult”, “difficult”, “easy”, “very easy”, “extremely easy”.

Anesthesia Assistant rating of perceived level of difficulty using the oxygen delivery device: The Anaesthesia Assistant will be asked to rate their perceived level of difficulty using the oxygen delivery device using

a 6-level rating scale with ratings of “extremely difficult”, “very difficult”, “difficult”, “easy”, “very easy”, “extremely easy”.

Comfort associated with oxygen delivery: Participants will be asked to rate at the end of procedures their perceived overall comfort with the oxygen delivery device used during the procedure using a 6-level rating scale with ratings of ‘maximal discomfort’, ‘very uncomfortable’, ‘uncomfortable’, ‘comfortable’, ‘very comfortable’ and ‘maximal comfort’.

Supplemental oxygen use and flow settings: Anesthesia Assistants will document their use of oxygen therapy in a case report form provided to them by the Research Assistant. Information on the FiO₂ setting, flow rate and temperature will be recorded in the HFNO group. The oxygen flow rate will be recorded in the control group.

Sedative medications: The Anesthesia Assistant will record the total doses of sedative medications used during procedures.

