The effects of the potential disadvantages of using HFNO during sedation should also be evaluated. It is possible that potential gains arising from delivering oxygen supplementation through the HFNO device may be offset by reduced ability to monitor ventilation from capnography waveforms when it is being used. Capnography

waveforms have not been validated for accuracy during HFNO therapy due to exhaled carbon dioxide being “washed out” by the high flows of gas.

The impact of using high flow nasal oxygen delivery systems routinely for conscious sedation on departmental costs is also unclear. Evidence from a pre-test post-test study of switching to routine use of HFNO in a critical care unit actually reduced departmental costs.¹³

In summary, although promising, further high-quality studies examining the effects of using HFNO during procedural sedation are required to inform decision-making regarding implementation of this new technology into practice. The 2018 guidelines from the American Society of Anesthesiology stated that there is insufficient evidence regarding which methods of supplemental oxygen administration (e.g., nasal cannula, face mask, or specialized devices such as HFNO) are more effective. This trial will address this limitation in the evidence base specifically in regard to the efficacy of using HFNO during conscious sedation in the cardiac catheterisation laboratory. Results from our study will provide clinical evidence regarding the effects of HFNO on ventilation in sedated patients.

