3.12 Statistical methods

3.12.1 Outcomes

For the primary outcome, peak TcCO₂ will be compared between the intervention and control groups using a Bayesian hierarchical model with baseline TcCO₂ concentration included in the model as a covariate as is recommended for this type of design.²⁶ Bayesian models will also be used to compare secondary outcomes among the randomization groups. Prior distributions for all model parameters will initially be chosen to be non-informative and will be adjusted as necessary to improve model fit. The posterior distributions of parameters and quantities of interest will be presented as well as their medians and 95% highest-density intervals (HDI). Subgroup analyses will be conducted to compare the effects of HFNO with standard care in patients who have a diagnosis of sleep apnea and those who have a cardiac resynchronization therapy device implant (the variables used for stratification) by including these variables in the model as interaction terms.

In addition to comparing the peak TcCO₂, per-second TcCO₂ levels will be compared between randomization groups using methods of functional data analysis. Functional observations will be estimated by fitting a B-spline basis to the TcCO₂ data, subject to a roughness penalty on the second derivative of the estimated function. Common features of these estimated functions will be examined using functional principal component analysis (FPCA). A formal comparison of TcCO₂ levels between randomization groups will be performed using functional analysis of variance (FANOVA). Results of this functional analysis will be compared to those obtained in the bayesian analysis on just the peak TcCO₂ levels.

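### Recorded sedation events (TROOPS) can differ between arms through detection alone, in either direction, and the plan has no safeguard against it

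*Combined protocol and SAP*

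**What the plan says.** **Who records events.** The trial summary lists adverse sedation events as a secondary outcome measured with TROOPS. Section 3.10.1 has the Anesthesia Assistant identify and describe each event, its management, outcome and severity: "The Anaesthesia Assistant will be asked to complete this tool at the end of procedures". Section 3.4 describes the same outcome only as nasal and skin effects and does not name TROOPS.

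**Who is blinded.** Section 3.9.1 says "participants or personnel involved in the trial cannot be blinded to the treatment conditions". Its one promise of blinded assessment is that "the primary outcome assessment for comparisons between groups will be made without knowledge of the assigned treatment allocation".

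**What can be seen at the bedside.** Section 2.1 raises the possibility that HFNO's gains are offset by "reduced ability to monitor ventilation from capnography waveforms when it is being used". It adds that capnography "waveforms have not been validated for accuracy during HFNO therapy due to exhaled carbon dioxide being" flushed away by the gas flow. For TcCO₂, section 3.10.1 says "the monitor will be covered with a drape so that it is not visible to research staff or clinicians during the procedure". SpO₂ "will be measured continuously throughout procedures as part of routine clinical practice through the anaesthetic machine", and is downloaded for the study.

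**How events are analysed.** Section 3.12.1 says only that "Bayesian models will also be used to compare secondary outcomes among the randomization groups". Section 3.12.2 rules out additional analyses.

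**The concern.** An event enters TROOPS only if the assistant recognises it. If one of the assistant's means of recognising hypoventilation works less well under one device, the recorded counts mix how often events happen with how often they are noticed. The assistant also knows which device is in use.

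What is at stake is the reading of the safety comparison. Section 2.1 says the possible disadvantages of HFNO should be evaluated, and names weaker ventilation monitoring as one of them. If that disadvantage is real, it could show up as fewer recorded events under HFNO and be reported as a benefit. The opposite error is also possible: a flat waveform caused by gas flow could be recorded as apnea and count against HFNO.

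**Working it through.** **1. The plan's own figures.** The plan states no figure for TROOPS events. Its only sample size is for peak TcCO₂ (section 3.6: difference 4 mmHg, SD 7 mmHg, 5% type I error, 90% power). Per arm, n = 2 × (1.96 + 1.2816)² × 7² / 4² = 64.4, rounded up to 65, so 130 in total. This reproduces the plan. Recruitment of 150 at 1:1 gives 75 per arm, which is used below.

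**2. Does equally recorded information close the gap?** Only in part.
- SpO₂ is recorded alike in both arms. However, section 2.1 says that in this setting desaturation is rare, while raised arterial carbon dioxide is common and points to hypoventilation. SpO₂ therefore covers the rarer problem.
- TcCO₂ does capture hypoventilation, but the assistant cannot see it, so it cannot help in identifying TROOPS events.
- Actions taken are not fully neutral. Section 3.3.1 allows the HFNO oxygen fraction to be raised on evidence of hypoventilation, so acting also depends on noticing.

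**3. How large could the effect be?** Every input here is an assumption: true risk p equal in both arms, facemask detection 0.90, HFNO detection s, 75 per arm. Detection is averaged over all event types, so events recognised from SpO₂ or clinical signs pull s towards 0.90.

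Recorded risk = p × detection, so the recorded risk ratio is s / 0.90 whatever p is. With p = 0.20, the facemask arm has 0.20 × 0.90 = 0.18, or 13.5 expected patients with an event.

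| HFNO detection s | Recorded HFNO risk | Risk ratio | Expected HFNO count | Chance of a nominally significant result favouring HFNO |
|---|---|---|---|---|
| 0.90 | 0.18 | 1.00 | 13.5 | 2.5% |
| 0.80 | 0.16 | 0.89 | 12.0 | 5.1% |
| 0.70 | 0.14 | 0.78 | 10.5 | 9.8% |
| 0.60 | 0.12 | 0.67 | 9.0 | 17.5% |
| 0.45 | 0.09 | 0.50 | 6.8 | 36.3% |

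The last column uses a two-sided 5% comparison of two proportions. It stands in for a 95% interval that excludes no difference, because the plan's Bayesian model for this outcome is not specified. At p = 0.05 and s = 0.60 the expected counts are 3.4 and 2.2, and the chance is 7.0%.

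**4. Direction.** Let f be the proportion of event-free HFNO patients in whom a flushed-out waveform is recorded as an event. The recorded HFNO risk becomes p × s + (1 − p) × f. The two errors cancel when f = p × (0.90 − s) / (1 − p). For p = 0.20 and s = 0.60, f = 0.06 / 0.80 = 0.075. Above 7.5%, the false difference goes against HFNO.

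**The case against.** **The protocol's wording is cautious.** A reader might infer that the protocol itself declares capnography unreliable under HFNO, and hence that the counts will differ. The text does not support this. Section 2.1 speaks of a possibility and of waveforms that have not been validated, so the documents support *can differ*, not *do differ*.

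**The causal chain is incomplete.** Capnography is mentioned only in the background. No section says that assistants use it to identify TROOPS events, and the tool's respiratory items are not listed. Events recognised from SpO₂, clinical signs or the need to act may not depend on it. This stands: it leaves the size unknown, although it does not show the risk to be absent.

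**Ventilation is already measured objectively.** Peak, mean and trajectory of TcCO₂, and the SpO₂ desaturation area, are machine-recorded in both arms, and the stated objective is ventilation. A reader might infer that the trial's main conclusion is at risk, and it is not. But nothing in the plan requires the event counts to be read beside those data.

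**Dropping capnography-only events can itself bias the comparison.** Detection route arises after randomisation and depends on arm. If capnography prompts early action in facemask patients, events that would later have shown in other ways would be removed from that arm. The same unblinded assistant would also record the route. This stands, and it is why the restricted set should be a sensitivity analysis and not replace the main comparison.

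**Conclusion.** The point holds as a possibility that the plan leaves open. An unblinded assistant identifies events, the protocol names a possible monitoring loss specific to HFNO, the TcCO₂ display is covered, and no arm-neutral event definition, adjudication or sensitivity analysis is described for TROOPS.

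The documents do not give the size. Under the assumed inputs above, the recorded risk ratio runs from 1.00 (no distortion) to 0.50 with no true effect, and false alarms could reverse the direction. The figures illustrate the range and do not estimate what will happen. Peak TcCO₂ and the sample size of 130 (150 recruited) are unaffected. This is a cheap improvement to a secondary safety comparison and does not put the trial's main result in doubt.

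**What to change.** 1. **Form.** Add a tick-all-that-apply field to the TROOPS form for how each respiratory event was recognised: capnography, SpO₂, clinical observation. Record any action taken in a separate field.
2. **Analysis.** Keep the comparison of all events. Prespecify a sensitivity analysis that excludes only events recognised by capnography alone, with no SpO₂ change, clinical sign or action. List the excluded events by arm. Amend section 3.12.2 to allow this.
3. **Interpretation.** Prespecify that respiratory event counts are read beside the downloaded SpO₂ and a hypoventilation measure derived from the covered TcCO₂ recording, using one analysis threshold fixed before analysis. Such a measure should not be too sparse. Treating peak TcCO₂ as normal with the preliminary study's mean of 46.8 and SD of 6.9 (Table 1), about 60% of patients would exceed 45 mmHg (z = −0.26) and about 32% would exceed 50 mmHg (z = 0.46). These cut-points are illustrations only.
4. **Consistency.** Name TROOPS under adverse sedation events in section 3.4, so that it agrees with the trial summary and section 3.10.1.

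**Cost.** The change needs the added form fields, a short addition to section 3.12 and a small extra analysis of data already recorded. The restricted set may contain few events, and the detection field is still completed by an unblinded assessor. It has to be recorded at the time, because the route of recognition is hard to reconstruct afterwards.
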